Yoga for generalized anxiety disorder: A comparison between yoga, cognitive behavioral therapy, and stress education training

Objectives

The general purpose of the study is to determine whether yoga is an effective method for treating GAD, and its relative efficacy compared to a standard psychosocial intervention. Our primary objective is to examine the short-term treatment efficacy of yoga on GAD symptoms. Our secondary objective is to examine the long-term treatment efficacy of yoga on GAD symptoms. Our tertiary objective is to examine and compare the mechanism of treatment changes in yoga and traditional CBT for GAD.

Design and Outcomes

This five-year multi-site study will examine the comparative efficacy of yoga, CBT, and stress education, a previously employed control condition, for patients with GAD. Across 2 enrolling centers (BU and MGH) we will randomize 230 patients with GAD to one of three 12 session weekly study treatments: 12-weekly yoga (n=95), CBT (n=95), or stress education (SE: n=40). Independent clinical assessments will occur before the 12-session intervention phase, at mid-treatment, after the intervention, and at 6-month follow-up. All clinician-rated outcomes will be assessed by trained Independent Evaluators (IEs) blind to treatment assignment. Response (CGI-I of 1 or 2) will serve as the primary outcome measure alongside the SIGH A as the core secondary continuous measure. Secondary outcome measures also include the STAI, PSS, BDI-II and BAI, QOL, ISI, PSQI and PSWQ. The FFMQ, MCQ, pre-ejection period, and cortisol are examined as possible mediators of change. The Credibility/Expectancy Questionnaire will be administered to examine whether credibility and expectancy moderates therapy outcome. In addition, we will explore whether clinical characteristics (comorbid diagnoses) and demographic characteristics (age, sex, SES) are possible moderators. We hypothesize that Yoga and CBT will each be superior to SE at post-treatment FU, and Yoga and CBT will not differ based on equivalency analyses. We predict that treatment changes during yoga are mediated via changes in mindfulness and changes in vagal tone, whereas changes in CBT are mediated via changes in maladaptive cognitions.

Interventions and Duration

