Our study statisticians will set up the randomization table stratified by site and with variablesized permuted blocks (maximum block size will be 6 to minimize cohort effects). The variablesized permuted block randomization schedules will be generated by [name] (the supervising biostatistician) prior to enrolling the first subject into the study. Randomization will be stratified by site, and groups of 4-6 individuals will be randomized at a time to one of the 3 treatment conditions. Randomizations will be conducted in SAS using the procedures outlined by Efird (2011) [Efird, J. Blocked Randomization with Randomly Selected Block Sizes. *Int. J. Environ. Res. Public Health.*, *8*, *15-20.J.* The randomization code will be emailed by [name] (the trial statistician) to the study coordinator only when the randomization occurs, i.e. once the last participant of each group has completed baseline.

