9.6 Data Analyses

Primary Analyses

Our primary analyses will use mixed-effects regression models (MRMs) with a logistic linking function (a GLMM analysis) since our primary outcome measure (response to treatment, defined as CGI-I≤2) is dichotomous. Analyses of secondary outcomes will be performed using MRM. MRM and GLMM easily accommodate nesting of repeated observations within subjects, include all subjects with at least one assessment, and are the preferred method to analyze longitudinal data (Hamer and Simpson, 2009 [135]). Since these analyses will include all subjects who are randomized and complete at least one assessment, it is an intent-to-treat analysis. Also, since subjects will undergo treatment in groups (4-6 subjects per group) our MRM and GLMM models will include 3 levels: repeated measurements (level 1) nested within subjects (level 2) who will be nested within their treatment cohort (level 3).

Our primary model will be a GLMM in which response to treatment over time will be modeled as a growth curve. Our primary analyses will examine outcomes at post-treatment (Aim 1). These analyses will include only the 7 assessments from baseline to post-treatment, and will not include the follow-up (FU) assessment since it could be affected by subjects seeking other treatments during the FU period. Only our exploratory analyses for outcome at FU (Aim 2) will include data from the FU assessment. Since recent research indicates that suboptimal modeling of the growth curve can result in incorrect results, we will examine various linear and nonlinear models to find the optimal growth curve during treatment (linear, quadratic, cubic, exponential [leveling off at an asymptote], and an ANOVA model, in which time is coded as a categorical variable. For this ANOVA model, each assessment time point is modeled with a dummy coded assessment variable [coded 1 for the assessment, 0 for other assessments]. In this model, the means at each assessment point are freely estimated and are not constrained to fit any particular pattern. See our discussion of the ANOVA model in the paragraph below for more information).We will conduct our significance tests using the growth curve that most accurately models the data (comparing the various growth curve models using AIC and BIC).

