The three treatment conditions (Yoga, CBT, and SE) will be coded using 2 dummy variable contrasts, with SE as the "reference" treatment. The first dummy variable will contrast Yoga vs. SE, and the second will contrast CBT to SE. Time will be coded as weeks since baseline. To test of differences between treatments at post-treatment (week 12), time will be centered at week 12 (in other words, our Time variable in our analysis will be computed as "time minus 12"). In MRM or GLMM analyses in which this Time centered variable is used, the significance of the dummy variable contrasts (Yoga vs. SE and CBT vs. SE) provides the test of the differences between treatment conditions at post-treatment. A similar approach can be used to test differences between treatment conditions at follow-up.

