This growth curve model will be used to test differences between treatment conditions for our primary outcome (response to treatment) and for CGI-S, since these outcomes are measured frequently enough (7 times during treatment) to accurately model the growth curve. However, the other secondary outcomes are measured at most3 times during treatment (baseline, week 6, post-treatment), with secondary sleep measures administered only twice (baseline and posttreatment), thus disallowing accurate assessment of their growth curve. Thus, these outcomes will use an MRM employing an ANOVA type design (see for example, Liu, Rovine, & Molenaar, 2012). In this kind of model, time is treated as a categorical variable (using2 dummy variables [one for each assessment except the baseline assessment] to code the 3 assessments). The three treatment conditions (Yoga, CBT, and SE) will be coded using the 2 dummy variable contrasts (Yoga vs. SE and CBT vs. SE). Interactions will be formed between each treatment condition contrast and each assessment dummy variable. This coding freely estimates the means for the outcome at each assessment, without any constraint from a specific growth curve. This design is similar to a 3 x 3 repeated measures ANOVA with the exception that it includes all patients that complete at least one assessment, the outcome can be dichotomous, the covariance structure of the repeated measures can take almost any form, and this approach assumes data are missing at random (MAR) or not missing completely at random (MCAR). The significance of the interaction between a treatment condition contrast (e.g., Yoga vs. SE) and an assessment dummy variable (e.g., for the post-treatment assessment) will test whether the change from baseline to that assessment is significantly different between the treatment conditions. Using this coding scheme, all contrasts between treatment conditions at all assessments are provided by this one analysis. Thus, this approach has the added benefit of having all contrasts between the treatment conditions at each assessment being conducted on the same sample.

Demographics and comorbid diagnoses will be used as covariates in all analyses and considered as possible moderators of outcome at each assessment. An additional moderator that will be investigated is homework adherence.

Planned Secondary Analysis of Sensitivity of Growth Curve Model for Primary Outcome

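### Section 9.6 does not state the cohort-level random effects; fitted as a cohort intercept, they cancel from the change-from-baseline tests and only partly cover the week-12 growth-curve contrasts

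*Combined protocol and SAP*

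**What the plan says.** Section 9.6 recognizes the issue: "subjects will undergo treatment in groups (4-6 subjects per group"), and the MRM and GLMM models are therefore given three levels, "repeated measurements (level 1) nested within subjects (level 2) who will be nested within their treatment cohort (level 3"). That is the whole specification of level 3. No cohort intercept, cohort slope, cohort-by-assessment effect or degrees-of-freedom rule is named.

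Two kinds of test follow in the same section:

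- For response and CGI-S, a growth curve in which "time will be centered at week 12", so that the arm dummies give the post-treatment comparison. "These analyses will include only the 7 assessments from baseline to post-treatment".
- For the other secondary outcomes, time is categorical, and the interaction of arm with an assessment dummy "will test whether the change from baseline to that assessment is significantly different between the treatment conditions".

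Section 4.3 adds that "groups of 4-6 individuals will be randomized at a time to one of the 3 treatment conditions", and that the code is released only after the last member of the group has finished baseline.

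**The concern.** A cohort random intercept is one constant per cohort, the same at every visit. The clustering that group treatment creates is different. Members share an instructor and a group only after baseline, so the shared effect starts near zero and is present at week 12, where the arms are compared. A constant cannot represent this in a change score, and in a growth curve it averages over early visits at which little has yet been shared.

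At stake are the Yoga vs SE and CBT vs SE comparisons. If level 3 does not reach the tested contrast, the analysis appears to allow for group treatment while intervals are too narrow and false positives too frequent. SIGH-A, named in Section 9.5.1 as the core continuous secondary measure, would be among the outcomes affected.

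**Working it through.** **Inputs**

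- Cohort size m = 5, the middle of 4-6 (Section 9.6).
- Arms: "12-weekly yoga (n=95), CBT (n=95), or stress education (SE: n=40") (Précis). Cohorts: 95/5 = 19, 95/5 = 19, 40/5 = 8; total 46.
- Assumed because not stated: two-sided 5% superiority tests; within-cohort correlation ρ of 0.02, 0.05 or 0.10; a shared effect that is zero at baseline.

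**The plan's own figure.** The documents give no error rate or cohort correlation for the clustered models. The sample size in Section 9.2 does not imply one either. With 57.9% response in both arms, margin 17.85 points, 80% power and one-sided 5% (the level is not stated), n = (1.645 + 0.842)² × 2 × 0.579 × 0.421 / 0.1785² = 94.6, or 95 per arm. The plan's 95 is therefore reproduced with patients treated as independent.

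**Cancellation.** Under an intercept-only level 3, patient i in cohort k at visit t has

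Y = μ(t) + c_k + s_i + e_it.

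The change to week 12 is μ(12) − μ(0) + e_i,12 − e_i,0. Both c_k and s_i have gone, exactly so with complete visits and whatever the variance of c_k.

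**Size for the change tests.** If changes within a cohort have correlation ρ, the variance of an arm's mean change is the independent-patient value times 1 + (m − 1)ρ = 1 + 4ρ. The reported SE is the true SE divided by √(1 + 4ρ), and the rejection rate is 2·P(Z > 1.96/√(1 + 4ρ)).

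| ρ | 1 + 4ρ | model SE / true SE | 1.96/√(1 + 4ρ) | rejection rate |
|---|---|---|---|---|
| 0.02 | 1.08 | 0.96 | 1.89 | 5.9% |
| 0.05 | 1.20 | 0.91 | 1.79 | 7.4% |
| 0.10 | 1.40 | 0.85 | 1.66 | 9.8% |

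**Simulation of the change test.** REML fits at weeks 0, 6 and 12 used 8/19/19 cohorts of 5, with the cohort effect rising linearly from zero (1,500 trials per value). Here the correlation is set at week 12 rather than on the change, so agreement with the formula need only be approximate.

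- Correlation 0.05: the SE is 0.191 both with a cohort intercept and with no cohort level; the true SD is 0.211. Yoga vs SE rejects 8.0%.
- Correlation 0.10: the SE is 0.193 in both fits; the true SD is 0.239. Rejection is 10.8%.
- With a time-varying cohort effect added, rejection is 4.5% and 5.7%.

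**CGI-S-type linear growth curve, 7 assessments (600 trials).** With a cohort intercept the SE is 0.221 against a true 0.243 at 0.05, and 0.227 against 0.282 at 0.10. Rejection is 8.3% and 12.0%. A separate analytic approximation gave 7.7% and 9.4%. A time-varying cohort effect gives 6.0% and 7.0%; the remaining excess is consistent with a z test resting on only 8 SE cohorts.

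**Primary response GLMM, correlation 0.10.** CGI-I is not collected at baseline (Section 6.1 footnote), so weeks 2-12 were used.

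- 220 trials: SE 0.51 with no cohort level, 0.54 with a cohort intercept, true SD 0.60. The intercept recovers (0.54 − 0.51)/(0.60 − 0.51), about one third of the shortfall. Rejection is 7.7%, with Monte Carlo SE √(0.077 × 0.923/220) = 1.8 points.
- 1,000 trials per setting: 9.5% with a cohort intercept (SE 0.57, true 0.65), 7.6% with a time-growing cohort effect, 6.3% when there is no clustering at all.

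**The case against.** The strongest reply is that Section 9.6 never says intercept-only. It names no random effects at any level, and a three-level model with a cohort slope fits the same sentence. This stands: the intercept is the likely default, not a documented choice. It does not clear the plan, because the wording permits a fit that gives the change tests no protection. The remark that "the covariance structure of the repeated measures can take almost any form" does not settle it, since it concerns measurements within a patient and not the cohort level.

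The second reply is that the primary analysis is largely spared. A reader might infer that group treatment is absent from the error bars throughout. The documents do not support that: even an intercept captures part of the clustering in the response GLMM, and there is no baseline CGI-I visit with zero effect to dilute it. The simulated excess is also imprecise. Part of it is present without clustering (6.3%), and the gain from the time-growing effect, 9.5% to 7.6%, has a Monte Carlo SE of about 1.25 points if the runs are independent. If the cohort effect is already full by week 2, the dilution is smaller still.

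Third, the size rests on assumed correlations, and at 0.02 the harm is small. That also stands.

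Finally, cohorts may be alike before treatment because they are assembled by site. This is a reason to keep a cohort intercept alongside any post-baseline term. It does not make the intercept sufficient.

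**Conclusion.** The concern holds as a conditional one. Level 3 is under-specified, and its ordinary fit leaves the change-from-baseline tests with the standard errors of a model that has no cohort level. For SIGH-A and the other outcomes tested by change, the false-positive rate is about 5.9%, 7.4% or 9.8% at assumed correlations of 0.02, 0.05 or 0.10. For CGI-S it is about 8% at 0.05 and 9-12% at 0.10 if the cohort effect grows over time. For the primary response contrast, coverage is partial and the inflation modest and uncertain, about 8-9.5% at 0.10.

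All of these figures assume an intercept-only fit, cohorts of 5 and clustering that arises after baseline. It would go too far to say that the plan ignores clustering or that its intervals are certainly too narrow: it sets up a cohort level, leaves its form open, and gives no correlation from which the size could be fixed. The point should still be settled before analysis, because the natural fit of the stated model is too optimistic for contrasts the plan intends to test.

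**What to change.** State the level-3 random effects in Section 9.6:

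- Categorical-time MRM: keep a cohort intercept and add cohort-by-assessment random effects on the post-baseline visits.
- Growth curves for response and CGI-S: a cohort intercept plus a cohort slope, with time centered at week 12.
- Inference: small-sample degrees of freedom reflecting about 46 cohorts, about 8 of them in SE.
- Convergence fallback, named in advance: a single cohort effect acting after baseline.

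The cost is SAP wording and a few extra variance terms. Intervals for the change tests widen by √1.08 − 1 = 4% at a correlation of 0.02 and √1.40 − 1 = 18% at 0.10, which is their correct width under those correlations.

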6.2.4 Follow-up Visits

At mid-treatment visit (week 6 after enrollment), post-treatment assessment (Week 12-13) and 6month follow-up (Week 36-27):

- Clinical improvement (CGI-I)
- Self-report instruments (STAI, BDI-II, BAI, PSS, SCL-90, WHOQOL-BREF, MCQ, FFMQ, PSWQ, ISI, PSQI, ASQ)
- Psychophysiological/biological measures of stress (RSA, cortisol)
- Measures of study integrity and safety (Adverse Events, Concomitant Medications/Therapy log. homework compliance, working alliance)

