7.1 Specification of Safety Parameters

A study MD or nurse with MD oversight will assess medical history and with consent will consult with PCPs if any medical issues that may potentially interfere with safe participation in yoga are identified. We have modified our study criteria to more clearly exclude all potential subjects with physical disabilities (evaluated with a medical history and physical exam) or cognitive disabilities (evaluated by the Montreal Cognitive Assessment Scale) that would clearly preclude safe practice of the yoga intervention or CBT. At present there is insufficient information regarding the safety of yoga during pregnancy. For reasons of safety, all women of childbearing potential will be required to use a reliable form of birth control throughout the study: (e.g.: oral contraceptives, surgical sterilization (of the subject or of her male partner), IUD (intrauterine device), condom and spermicide or diaphragm and spermicide). Subjects with existing or planned pregnancy during the intervention will be excluded. Inclusion of subjects

with any minor preexisting conditions of potential concern will be subject to participation only after consented review with and approval by the subject's primary healthcare provider.

Each visit, adverse events will be assessed on the adverse events monitoring form and rated as mild, moderate, or severe (as defined in AE section below). On weeks 0, 2, 4, 8, 10 and 12 the CGI-S, CGI-I, BDI and a suicidality checklist will be administered to evaluate any potential worsening symptoms. Physical fitness will be assessed by the study nurse with MD oversight or MD with the medical history form and a standard physical exam, emphasizing musculoskeletal, neurologic and cardiac history.

Twenty-four-hour emergency coverage with a study clinician (physician, psychologist or registered nurse with MD oversight) will be available. Patients will be provided with cards with the emergency contact number. In the event of an emergency the clinician will determine the necessary clinical intervention and will provide and coordinate appropriate care.

Parameters

All three interventions (Yoga, CBT, and SE) are safe interventions with minimal associated risk.

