9.2 Sample Size and Randomization

A non-inferiority test is the most direct test of our hypothesis that Yoga will be as effective as CBT for both short-term and long-term outcomes. We will perform a non-inferiority test using response rate (response rate is defined as CGI-I ≤ 2) as the outcome on which to compare CBT and Yoga at posttreatment and at follow-up. Since some attrition may occur, we will use last observation carried forward to insure an intent-to-treat analysis. The non-inferiority margin will be half the difference in response rates between the active comparison (CBT) and placebo. Based on earlier literature, we can expect response rates in our particular CBT and placebo conditions of 57.9% in CBT and 22.2% in placebo. Thus, our non-inferiority margin will be set at ¹/₂ the difference between 56.7 and 22.2, or 17.85%. Using the power analysis program PASS 12, we find that the number of subjects required to obtain .80 power for the non-inferiority test comparing CBT and Yoga is 95 participants in each of the 2 conditions. We verified this number in a 1000 simulation Monte Carlo study using these same parameters. This number is higher than the number proposed in the original grant. Thus, we will increase the N per cell in CBT and Yoga to 95 (22 additional patients per site) to have adequate power for this non-inferiority test. While the original study was budgeted based on a lower number of participants, with careful management of costs we believe we can manage this increase in participants within the full study budget if awarded as proposed.

For the superiority tests (CBT vs. SE and Yoga vs. SE) on the secondary outcomes (which are continuous), we used the MRM power analysis program PinT 2.12. We assumed 25% missing data, and used data from our recent CBT trials (e.g., Stern et al., 2012) to estimate the variances and covariances needed for PinT. PinT indicated greater than .80 power to detect an effect size as small as d=.27, between a small (d=.20) and medium (d=.50) effect size.

We predict that changes in mindfulness will mediate changes in outcome over time for patients in the Yoga condition, and changes in cognitions will mediate changes in CBT. Plus, changes in RSA and cortisol may also mediate changes in outcome across conditions. We further predict that treatment condition will moderate the effect of Time on the mediators ("a" paths).

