9.3 Definition of Populations

Our primary analyses will use mixed-effects regression models (MRMs) with a logistic linking function (a GLMM analysis) since our primary outcome measure is dichotomous (treatment response). Analyses of secondary outcomes will be performed using MRM. MRM and GLMM easily accommodate nesting of repeated observations within subjects, include all who complete at least one assessment (including the baseline assessment), and are the preferred method to analyze longitudinal data (Hamer and Simpson, 2009 [135]). Our intent-to-treat sample includes all randomized patients who complete at least one assessment. Thus, our primary analyses (GLMM and MRM) are intent-to-treat analyses. We will also perform "per protocol" analyses. Our per protocol population will include all randomized patients who complete the baseline and post-treatment assessments, miss no more than 2 treatment sessions, who average a 4 or higher on the homework compliance scale, and who did not initiate prohibited treatment during the study. We will repeat our GLMM and MRM analyses using the per protocol sample.

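### The primary response model is specified on seven assessments, but CGI-I response has six, and patients with only a baseline visit are called intent-to-treat without any response value or rule to supply one

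*Combined protocol and SAP*

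**What the plan says.** Section 9.6 bases the primary GLMM on response and says: "These analyses will include only the 7 assessments from baseline to post-treatment". It later justifies a growth curve for response and CGI-S together because "these outcomes are measured frequently enough (7 times during treatment) to accurately model the growth curve". Response means a CGI-I of 1 or 2 (Section 9.5.1).

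The visit lists do not agree with this or with each other. The Section 6.1 schedule shows CGI-S and CGI-I on one row, and footnote 1 removes CGI-I from screening and baseline. Section 6.2.4 places CGI-I at week 6: "At mid-treatment visit (week 6 after enrollment), post-treatment assessment (Week 12-13". Section 7.1 has a different list: "On weeks 0, 2, 4, 8, 10 and 12 the CGI-S, CGI-I, BDI and a suicidality checklist will be administered".

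On the analysis set, Section 9.3 says the models "include all who complete at least one assessment (including the baseline assessment", and Section 9.6 concludes: "Since these analyses will include all subjects who are randomized and complete at least one assessment, it is an intent-to-treat analysis". Section 3 commits to analysing every randomized participant. For the non-inferiority test, Sections 9.2 and 9.5 say "we will use last observation carried forward to insure an intent-to-treat analysis", and the logistic sensitivity analysis in Section 9.6 uses the same device. Section 9.2 gives the sample size: "the number of subjects required to obtain .80 power for the non-inferiority test comparing CBT and Yoga is 95 participants" in each of the two arms.

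Section 9.2 names site as the only stratification factor. Section 9.6 adjusts all analyses for demographics and comorbid diagnoses. It uses baseline CGI-S and SIGH-A only in the secondary logistic regression.

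**The concern.** CGI-I measures change since baseline, so it has no baseline value. A plan that asks for seven response assessments from baseline asks for one that does not exist. If the week-0 rows stay empty, the model drops them and no estimate changes. The risk is that an analyst sets week-0 response to 0 for everyone to reach seven. The plan neither states nor forbids this. It would pull the fitted curve towards zero at the start, could move the week-12 estimate, and could change which curve wins on AIC and BIC.

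The intent-to-treat claim fails for the same reason. It holds for CGI-S, where the baseline value is an outcome row. It does not hold for response, because a baseline-only patient has no outcome row. Carrying forward does not help, since there is no earlier CGI-I to carry. The analyst must then choose between leaving such patients out, counting them as non-responders, or imputing them. The non-inferiority test is sensitive to that choice, and its planned size has no slack.

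**Working it through.** **1. Count of assessments.** In the Section 6.1 schedule, biweekly ratings in weeks 1-5 and 7-11 fall at weeks 2, 4, 8 and 10; week 6 and post-treatment (week 12) are added.
- CGI-S: weeks 0, 2, 4, 6, 8, 10, 12 = 7. The plan's figure reproduces.
- CGI-I response: the same list without week 0 = 6. The plan's figure does not reproduce.
- Section 7.1: weeks 0, 2, 4, 8, 10, 12 = 6 entries. It includes week 0, against footnote 1, and omits week 6, against Sections 6.1 and 6.2.4. Neither list gives seven CGI-I ratings.
- The extra weekly ratings triggered by a CGI-I of 5 or more (footnote 2) apply to individuals and are not a seventh common visit.

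**2. Effect of coding week 0 as non-response.** This is an illustration with assumed response paths, using a simple linear-logit fit and not the full three-level model. The paths end at the planned 57.9% (CBT) and 22.2% (SE). One rises linearly; the other levels off in proportion to 1 − exp(−week/3).

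| Path | Arm | Fitted week 12, six visits | Fitted week 12, week 0 set to 0 |
|---|---|---|---|
| Linear | CBT | 0.600 | 0.627 |
| Linear | SE | 0.238 | 0.254 |
| Plateau | CBT | 0.624 | 0.685 |
| Plateau | SE | 0.242 | 0.274 |

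The CBT-SE difference moves from 0.600 − 0.238 = 0.362 to 0.627 − 0.254 = 0.373 (linear), and from 0.624 − 0.242 = 0.382 to 0.685 − 0.274 = 0.411 (plateau).

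**3. The planned non-inferiority size.** Inputs from Section 9.2: response 57.9%, margin 17.85 points, power 0.80. The margin equals (57.9 − 22.2)/2 = 17.85; the 56.7 printed beside it would give 17.25 and looks like a slip. No alpha is stated.
- n per arm = 2 × 0.579 × 0.421 × (z_alpha + 0.842)² / 0.1785².
- One-sided 0.05 (z = 1.645): 94.6, rounded up to 95. The plan's figure reproduces.
- One-sided 0.025 (z = 1.960): 120.1, rounded up to 121. It does not.

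**4. Power if unrated patients are left out.** One-sided 0.05 is assumed. Power = Φ(0.1785/SE − 1.645), with SE = √(2 × 0.579 × 0.421/n).
- n = 95: SE 0.0716, Φ(0.847) = 0.801.
- n = 90: SE 0.0736, Φ(0.780) = 0.782.
- n = 76: SE 0.0801, Φ(0.584) = 0.720. This is the extreme in which all of the 20% expected to discontinue (Section 3) have no post-baseline rating.

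**5. Effect of counting them as non-responders.** With k of 95 unrated in each arm, and assuming they would have responded like the rated patients, each arm's rate is multiplied by (95 − k)/95, and so is the difference. Take a true difference at the margin: CBT 57.9%, yoga 57.9 − 17.85 = 40.05%.
- k = 5: 17.85 × 90/95 = 16.91 points. The SE is 0.0713, so the chance of wrongly declaring non-inferiority is Φ((0.1785 − 0.1691)/0.0713 − 1.645) = about 6.5% instead of 5.0%.
- k = 10: 17.85 × 85/95 = 15.97 points, and about 8.4%.
- At one-sided 0.025 the corresponding figures are about 3.4% and 4.5%.

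**The case against.** The strongest reply is that footnote 1 already settles the matter: CGI-I is not given at baseline, a likelihood-based GLMM ignores rows with no outcome, and the seven is a harmless carry-over from CGI-S. Section 7.1 is a safety sentence giving one shared week list for four instruments, so its conflict with the schedule is a wording matter. Much of this stands. A reader might infer that the seven-assessment wording in itself biases the primary result; the documents do not support that. The wording does harm only if baseline is coded as non-response, which the plan leaves open.

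A reader might also infer that the categorical-time candidate cannot be estimated for response, because its treatment test is a change from baseline. Section 9.6 writes that baseline-reference coding for outcomes measured at most three times during treatment, and for the growth curves it places the treatment test at week 12. That inference is not supported.

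It can further be said that Section 8.1 encourages an endpoint visit after discontinuation and that Section 9.6 plans pattern-mixture reruns. The first reduces the number of unrated patients. The second shows whether findings depend on the dropout pattern. Neither says what response value a patient with no CGI-I receives, so the gap remains.

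On covariates, demographics and comorbid diagnoses are already included. Cohorts are randomized within site (Section 4.3), so the cohort effect can absorb part of the site variation. That limits the gain from adding site and severity but does not remove the case for it.

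**Conclusion.** The concern holds. For the primary outcome, the stated count is wrong (six, not seven). The statement that the GLMM is intent-to-treat for everyone with at least one assessment is also wrong, since baseline-only patients contribute nothing to it. No rule covers them in the carried-forward analyses, including the non-inferiority test.

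The size is uncertain because the documents do not give the number of patients with no post-baseline CGI-I. The 20% in Section 3 is discontinuation of the intervention at any time and cannot be read as that number, so a large loss of power should not be inferred. If five per arm were unrated and left out, power would fall from 0.801 to 0.782, given the assumed one-sided 0.05.

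A reader might suppose that equal numbers of unrated patients in the two arms cancel when counted as non-responders. They do so only if the two response rates are equal. Otherwise the arms are drawn together, which favours a finding of non-inferiority.

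Omitting site and baseline severity is a missed improvement. No bias is claimed, and the gain in precision is likely modest.

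**What to change.** - **Assessments.** State six post-baseline assessments for response and seven for CGI-S. Fit the response GLMM with no week-0 row, and say that baseline is not to be coded as non-response. Reconcile the CGI-I weeks in Section 7.1 with Sections 6.1 and 6.2.4.
- **Analysis set.** Correct Sections 9.3 and 9.6: the response GLMM includes randomized patients with at least one post-baseline CGI-I.
- **Unrated patients, non-inferiority test.** For patients with no post-baseline CGI-I, multiply impute week-12 response from arm, site and baseline severity. Report non-responder counting as a sensitivity analysis only, with a note that it shrinks any true difference. Imputation keeps these patients in the comparison; it should not be expected to restore the lost power.
- **Unrated patients, superiority regression.** Counting them as non-responders is acceptable in the carried-forward logistic regression against SE, if stated in advance.
- **Covariates.** Add site, baseline CGI-S and baseline SIGH-A as fixed covariates in the primary model.

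The pattern-mixture reruns can stay as planned. The cost is SAP wording, three covariates and a small amount of extra analysis on data already collected.
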